9.2.1.3. Tear Break-Up Time

A drop of Altafluor is added to the eye and the subject may blink for 2 seconds to disperse it. Then, while the subject avoids blinking, the tear film is observed under the slit lamp through a cobalt blue filter and timed until tiny dry spots develop. If there is break-up in the tear film immediately after the blink, this shall be registered as 0. The procedure is conducted 3 times for each eye and the TBUT for each is measured in seconds and recorded in the eCRF. The average for each eye will be calculated by the eDC system (see Study Procedures Manual).

9.2.1.4. Schirmer's Test (Anesthetized)

An anesthetized Schirmer's test will be performed to ensure that only basal tear secretion is being measured and to prevent tearing due to the irritation from the filter paper (the eyes will already have been anesthetized for the TBUT procedure). Schirmer strips will be placed in both eyes on the lower eyelid margins at the same time. The eyes are closed for 5 minutes. The strips are then removed and the amount of moisture on each strip in millimeters (mm) is measured and recorded in the eCRF (see Study Procedures Manual).

9.2.2. Symptoms

A laminated copy of the OSDI questionnaire ([Appendix A](#)) will be provided to the subject, who will be asked to point to the number that corresponds with the frequency of dry eye symptoms experienced over the past week. Site personnel will enter the scores in the eCRF. The eDC system will automatically calculate the final score.

9.3. Safety Assessments

9.3.1. Slit Lamp Examination

A routine slit lamp examination will be performed to evaluate the anterior segment of the eye, including lids, cornea, conjunctiva, anterior chamber, iris, and lens. Abnormalities will be documented.

9.4. Pharmacokinetic Assessment

9.4.1. HS-Omega-3 Index Test

The HS-Omega-3 Index Test measures the concentration of 2 specific omega-3 fatty acids, EPA and DHA, as a percent of total fatty acids in red blood cell membranes. This test is performed by using a contact-activated lancet to collect a drop or 2 of blood on a collection card. Each card is identified and packaged to be submitted to OmegaQuant (Sioux Falls, SD) for analysis.

9.5. Other Assessment

9.5.1. Vitamin Dosing Compliance Question

At the Final Study Visit, subjects will be asked the yes/no question, "During the study, did you regularly take any vitamins within 2 hours of taking your study medication?" Subjects who have already completed their Day 84 Final Study Visit at the time of this Protocol Amendment (V4.0) will be contacted by the site to establish their compliance with dosing of any vitamins (to be taken more than 2 hours before or after study medication) during the study.

9.6. Adverse and Serious Adverse Events

9.6.1. Definition of Adverse Events

9.6.1.1. Adverse Event

An AE is any untoward medical occurrence in a clinical study subject administered an IP (pharmaceutical/biological product) that does not necessarily have a causal relationship to this medication. An AE can therefore be any unfavorable and unintended sign (including abnormal laboratory findings), symptom, or disease temporally associated with the use of the IP, whether or not related to the IP. IP includes the investigational drug under evaluation and the comparator product or vehicle placebo that is given during any phase of the study.

Medical conditions/diseases present before starting the investigational treatment are only considered AEs if they worsen after starting the investigational treatment. Abnormal test results constitute AEs only if they induce clinical signs or symptoms, are considered clinically significant, or require therapy.

The occurrence of AEs should be sought by open-ended questioning of the subject at each visit during the study. At each clinic visit, study personnel should ask the following question: "Have you had any problems since your last visit?" AEs also may be detected when they are volunteered by the subject during or between visits or through study assessments.

9.6.1.2. Serious Adverse Event

An SAE is any untoward medical occurrence that at any dose:

- Results in death
- Is life-threatening or sight-threatening

Note: The term "life-threatening" refers to an event in which the subject was at risk of death at the time of the event; it does not refer to an event which hypothetically might have caused death if it were more severe.

- Results in persistent or significant disability/incapacity (excluding progression/outcome of the disease under study)
- Is a congenital anomaly/birth defect
- Requires inpatient hospitalization or prolongation of existing hospitalization, or
- Is medically significant (ie, defined as an event that jeopardizes the health of the subject or may require medical or surgical intervention to prevent one of the outcomes listed above)

Treatment on an outpatient emergency basis that does not result in hospital admission, or a hospitalization that is elective or is a preplanned treatment for a pre-existing condition that is unrelated to the indication under study and has not worsened since the start of the study, is not considered an SAE.

All SAEs that are ongoing at the time of completion or discontinuation from the study will be followed until stabilization (ie, no other change in the condition is expected) or resolution of the event.

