8.5. Discontinuation of Investigational Product

Subjects may be discontinued from IP for either of the following reasons:

- The subject has a clinically significant or serious AE that would not be consistent with continuation in the study, as determined by the Investigator or Medical Monitor

- It is possible for subjects to experience a skin rash or other allergic reaction related to the components of the softgels; if this occurs, the subject should discontinue the medication
- Pregnancy

If a subject is discontinued from IP or is generally noncompliant with the protocol, every effort should be made to encourage the subject to continue to attend study visits to be followed for safety, rather than withdrawing the subject from the study. Reasons for considering subject withdrawal from the study are discussed in [Section 7.3](#).

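### Protocol Section 9.6.1.2 contradicts itself on whether a life-threatening, sight-threatening or medically significant event treated as an outpatient emergency without admission is an SAE

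*Protocol*

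**What the plan says.** Section 9.6.1.2 of the protocol defines an SAE by six alternative criteria: death, threat to life or sight, persistent or significant disability, congenital anomaly, hospitalization, and medical significance. Three of them matter here.

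- "Is life-threatening or sight-threatening". A note under this item explains that the first term "refers to an event in which the subject was at risk of death at the time of the event". The place of treatment plays no part.
- "Requires inpatient hospitalization or prolongation of existing hospitalization, or". This is the only criterion that turns on admission. The closing conjunction shows that the list is one of alternatives.
- Medical significance, which includes an event that "may require medical or surgical intervention to prevent one of the outcomes listed above". Again no setting is named.

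A separate paragraph follows the whole list. It names two things. The first is "Treatment on an outpatient emergency basis that does not result in hospital admission". The second is an elective admission, or one for "a preplanned treatment for a pre-existing condition that is unrelated to the indication under study and has not worsened since the start of the study". Its predicate for both is that each "is not considered an SAE".

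Section 9.8 sends the decision on seriousness back to Section 9.6.1.2. Section 9.9 sets the reporting duties for SAEs. SAP Section 10 plans a table of SAEs beside the general AE tables.

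**The concern.** The closing sentence is worded as a limit on what counts as an SAE, not as a limit on the hospitalization criterion. An event that put a subject's life or sight at risk, was treated in an emergency department and ended in discharge is therefore serious under the list and non-serious under the sentence. The medically significant criterion is the most exposed, because successful emergency treatment without admission is a typical way of preventing one of the listed outcomes.

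The classification has consequences. The 24-hour report to the CRO, the SAE form, the SAE-based notification of FDA and the IRB, the serious field on the AE eCRF page and the SAP's SAE table all require that the site has called the event an SAE. Safety is part of the primary objective (Section 5.1). With about 15 sites planned, an unresolved definition can also be applied differently from one site to another.

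**Working it through.** No arithmetic applies. The plan gives no figure on this point, and the issue does not depend on alpha, power, a standard deviation or an event rate. The check is to run types of event through both parts of Section 9.6.1.2, then look elsewhere for a rule that settles any conflict.

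**Step 1. Apply the list and the sentence separately, reading the sentence literally.**

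| Event | List of criteria | Closing sentence | Result |
|---|---|---|---|
| Life-threatening, emergency outpatient care, discharged | SAE | Not an SAE | Conflict |
| Sight-threatening, emergency outpatient care, no admission | SAE | Not an SAE | Conflict |
| Medically significant, emergency outpatient care, no admission | SAE | Not an SAE | Conflict |
| Emergency outpatient care, no criterion met | Not an SAE | Not an SAE | Agree |
| Emergency visit leading to inpatient admission | SAE | Does not apply | Agree |

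The sentence does its ordinary work in the fourth row. The trouble lies in the first three.

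**Step 2. Look for a qualifier inside the sentence.** There is one, on unrelatedness to the indication and absence of worsening. It belongs to the elective or preplanned limb. The outpatient emergency limb has none.

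**Step 3. Look at placement.** The note on the meaning of life-threatening sits under its own criterion, so the section does attach a clarification to a single item when it wants to. The closing sentence sits after all six items.

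**Step 4. Look for an order of precedence elsewhere.**

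- Section 9.8 points back to Section 9.6.1.2 and adds no rule of its own.
- Section 9.9 separately requires a death to be reported as an SAE. It makes no such provision for a life- or sight-threatening event that the subject survives.
- Section 8.2.1, on emergency unmasking, assumes that the event is an SAE and does not mention admission. It applies only when a subject is unmasked, and it fits poorly with a literal reading of the closing sentence.
- SAP Section 10 tabulates SAEs and does not redefine them.

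No passage resolves the first three rows.

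**Step 5. Separate what depends on SAE status from what does not.**

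- Dependent: the 24-hour SAE report, the SAE form, SAE-based FDA and IRB notification, the serious flag and the SAE table.
- Not dependent: recording on the AE eCRF page with severity, relationship and action taken (Section 9.8); follow-up to resolution after Visit 4 for AEs suspected to be related (Section 9.8); the sponsor's view of relationship, which Section 9.7 applies to AEs and SAEs alike; and the SAP's AE tables by severity and relationship.

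**The case against.** The best case for the current text is grammatical. The sentence speaks of treatment and of hospitalization, not of events, and both limbs concern admission. An experienced investigator may well read it as saying only that an emergency visit without admission, or an elective admission, does not count as hospitalization. Section 8.2.1 supports that reading. This is a plausible account of the intent, and it stands as such. It does not remove the conflict, because the predicate denies SAE status outright and nothing limits it to one criterion. If the narrow reading is intended, saying so costs nothing.

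There are also partial safeguards. Monitors review data remotely and flag safety signals to the Medical Monitor (Section 13.5), and unmasking triggers contact with the CRO within 24 hours for an AE or an SAE (Section 8.2.1). The first has no clock and the second applies only to unmasked subjects. Neither replaces the SAE report.

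A reader might infer three stronger things that the documents do not support.

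- That the protocol definitely rules such events non-serious. It does not: the list still makes them serious, and the text is in conflict.
- That such an event would drop out of safety follow-up altogether. It would not, as Step 5 of the working shows.
- That the absence of SAEs in the previous OmegaD trial (Section 4.2) can be turned into an estimate of how many events are at risk. A bound from that result would cover all SAEs, not those meeting a criterion and treated without admission.

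Finally, Section 8.5 does note that "It is possible for subjects to experience a skin rash or other allergic reaction related to the components of the softgels". It does not describe a life-threatening reaction, so it shows only that a reaction to the product is foreseen, not how severe one might be.

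**Conclusion.** The point holds as an internal contradiction in the SAE definition. A site that applies the closing sentence literally could withhold the 24-hour report and the serious flag from an event that meets a listed criterion, and the SAP's SAE table would be short by each event so classed. The event would remain visible as an AE.

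No size can be given. The documents contain no rate of life-threatening, sight-threatening or medically significant events treated without admission, and the expected number may be zero. The conclusion rests on the wording alone, and on the assumption that at least some sites would apply the sentence as written. The SAE form and the eCRF seriousness field are not among the documents, so whether they repeat the sentence is unknown.

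Randomization, endpoints, sample size and efficacy analyses are not affected. The correction is still worth making, because the definition governs expedited safety reporting.

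**What to change.** Reconcile the list and the closing sentence in Section 9.6.1.2. Suggested wording: *Emergency care given to an outpatient who is not then admitted, or an elective or preplanned hospitalization as described here, does not by itself meet the hospitalization criterion. An event that meets any other criterion in the list remains an SAE.*

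Check that the SAE form and the eCRF seriousness field say the same, and tell sites by memo. The SAP needs no change, since its SAE table takes the protocol's classification.

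The cost is one sentence in a protocol amendment, the memo, and possibly a few more SAE forms. No treatment, visit or analysis changes.

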9.7. Relationship to Investigational Product

The relationship of AEs to the IP should be assessed by the Investigator using the definitions below.

Not suspected: The temporal relationship of the event to the IP makes a causal relationship unlikely, or, other drugs, therapeutic interventions or underlying conditions provide a sufficient explanation for the observed event.

Suspected: The temporal relationship of the event to the IP makes a causal relationship possible or other drugs, therapeutic interventions or underlying conditions do not provide a sufficient explanation for the observed event.

If there is any valid reason, even if undetermined, for suspecting a possible cause-and-effect relationship between the IP and the occurrence of the AE, then the AE should be considered “suspected.”

If the relationship between the AE/SAE and the IP is determined by the Sponsor or designee to be “suspected,” the event will be considered to be related to the IP for the purposes of expedited regulatory reporting (see [Section 9.9](#)).

9.8. Recording Adverse Events

AEs spontaneously reported by the subject and/or in response to an open question from the study personnel or revealed by observation, regardless of severity or potential association with the IP or study procedures, will be recorded in the eCRF. Clinically significant changes in blood pressure and heart rate should be reported as AEs; however, omega-3 treatment has been demonstrated to have beneficial effects on blood pressure and heart rate. Only clinically significant changes (increase or decrease) in heart rate should be reported as AEs. All AEs that occur after a subject has signed the ICF until the Final Study Visit (Visit 4/Day 84), should be collected and recorded on the AE eCRF page. AEs that occur after informed consent is provided but before the first dose of IP will be summarized separately from AEs that occur from the first dose of double-masked treatment on Day 1 to the Day 84 Visit. Following Visit 4 (Day 84), all AEs “suspected” to be related to the IP should be followed until resolution.

Medical conditions/diseases occurring before the first dose of IP during Visit 2 (Day 1) should be collected on the medical/ocular history pages of the eCRF.

The AE term should be reported in standard medical terminology when possible. For each AE, the Investigator will evaluate and report the following:

- Onset date
- Resolution date
- Severity grade (mild, moderate, severe)
- Relationship to IP (not suspected, suspected)

- Action taken (none, IP temporarily interrupted, IP permanently discontinued; concomitant medication taken; hospitalization/prolonged hospitalization; other)
- Serious outcome (yes/no)

The severity grade should be determined by the Investigator using the definitions below:

- Mild: Discomfort noticed but no disruption of normal daily activity
- Moderate: Discomfort sufficient to cause interference with normal daily activity
- Severe: Incapacitating, with inability to perform normal activities

It is important to distinguish between serious and severe AEs. Severity is a measure of intensity (as defined directly above) whereas seriousness is defined by the criteria under [Section 9.6.1.2](#). An AE of severe intensity may not be considered serious.

Should a pregnancy occur, it must be reported and recorded on the pregnancy form. Pregnancy in itself is not regarded as an AE unless there is a suspicion that an IP may have interfered with the effectiveness of a contraceptive medication.

The outcome of all pregnancies (spontaneous miscarriage, elective termination, normal birth or congenital abnormality) must be followed up and documented even if the subject was discontinued from the study.

9.9. Reporting Adverse Events

All SAEs (suspected and not suspected) will be recorded from signing of informed consent until the Final Study Visit (Visit 4/Day 84), following the end of treatment exposure. Any SAEs “suspected” to be related to the IP and discovered by the Investigator at any time after the study should be reported to Oculos.

Any SAE that occurs must be reported to Oculos within 24 hours of its occurrence or within 24 hours of learning of its occurrence. Recurrent episodes, complications, or progression of the initial SAE must be reported to Oculos as follow-up to the original episode within 24 hours of the Investigator receiving the information. Information about all SAEs will be collected and recorded on the SAE form. All pertinent medical records and information collected during the treatment and follow-up of the subject should be maintained at the site with a copy emailed to [contact]. The Investigator must assess the SAE relationship and complete the SAE form. Oculos may request additional information. Follow-up information (eg, discharge summary) will be retained in the subject’s chart and a copy will be emailed to [contact].

In addition, all SAEs should be recorded on the AE eCRF page with the serious question marked “Yes”.

It is the Investigator’s responsibility to notify the approving IRB of any SAEs on a timely basis as instructed by the Sponsor or designee following the Sponsor’s determination of causality.

All subjects who experience an SAE should be followed clinically and undergo the appropriate diagnostic evaluations until stabilization or resolution of the event.

Oculos will report all SAEs to the US FDA on the appropriate schedule depending if the event is drug related or not drug related, expected or unexpected (based on the available information in the [Investigator's Brochure](#)).

Any death occurring during the study or follow-up period should be reported as an SAE. For any death occurring through the end of the study, regardless of the degree of relationship to IP, the SAE resulting in the death must be reported to Oculos. A death occurring after completion of the study at Visit 4 (Day 84) does not require completion of the SAE form.

10. STUDY ACTIVITIES

Note: Ophthalmic examinations should be conducted in the order listed in the Schedule of Procedures ([Table 2](#)). All ophthalmic examinations are conducted in both eyes. Subjects must not have used any ophthalmic drop within 2 hours and must not have worn contact lenses within 12 hours of the study visit. Subjects determined to have used ophthalmic drops or worn contacts within the specified durations prior to study visits must be rescheduled.

Note: For those subjects unable or unwilling to attend a scheduled study visit in-person during the COVID-19 pandemic, a “phone visit” will be conducted to allow collection of as many data points as possible, including changes to concomitant medication, AE inquiries, OSDI questionnaire responses, and response to the vitamin dosing compliance question. Subjects who are willing and able will be asked to come into the office for the Final Study Visit, during which all scheduled assessments will be conducted. Additional subject enrollment will occur to compensate for those subjects unable or unwilling to attend their Final Study Visit, to ensure a minimum of 300 evaluable subjects.

10.1. Visit 1 (Day -7 to Day -1)/Screening

At Visit 1 (Day -7 to Day -1)/Screening, subjects will provide written informed consent before any study-related procedures are conducted and will participate in screening procedures to establish eligibility for the study. Procedures performed at Screening will include the following:

- Obtain written informed consent
- Demographics
- Medical and ocular histories
- Concomitant medication history
- Urine pregnancy test (women of childbearing potential only)
- OSDI
- Tear osmolarity test
- Meibomian gland dysfunction grading
- Slit lamp examination
- TBUT
- Schirmer’s test (anesthetized)
- Review inclusion/exclusion criteria
- AE assessment

Only subjects with a score on the OSDI ≥ 20 , tear osmolarity ≥ 312 mOsm/L and meibomian gland dysfunction grade **1 or 2** on the meibomian orifice size scale in at least one eye, TBUT ≤ 7 seconds in both eyes and Schirmer’s test score (anesthetized) ≥ 5 mm in both eyes will be scheduled to return to the clinical site for Visit 2 (Day 1). The qualifying osmolarity level and meibomian orifice size grade must be present in the same eye at Screening if only one eye qualifies.

10.2. Visit 2 (Day 1)/Baseline

At Visit 2 (Day 1)/Baseline, the site will conduct confirmatory examinations of eligibility and subjects who continue to meet eligibility criteria will participate in baseline dry eye disease examinations, be randomized, and receive a supply of IP. Procedures performed at Baseline include:

- Concomitant medication review
- Urine pregnancy test (women of childbearing potential only)
- Tear osmolarity test
- Meibomian gland dysfunction grading
- Slit lamp examination
- Review inclusion/exclusion criteria to confirm eligibility. Subjects who do not meet the following criteria will be considered to have failed screening at this point:
 - Subjects must have tear osmolarity ≥ 312 mOsm/L and meibomian gland dysfunction grade as defined by a grade **1 or 2** on the meibomian orifice size scale **in at least one eye at both Screening and Baseline**. The qualifying osmolarity level and meibomian orifice size grade must be present in the same eye at both Screening and Baseline if only one eye qualifies
 - TBUT ≤ 7 seconds in **both eyes at Screening** (TBUT is not conducted at Baseline)
 - Schirmer's test score (anesthetized) at **Screening** must be ≥ 5 mm in **both eyes** (Schirmer's test is not conducted at Baseline)
 - OSDI ≥ 20 points at **Screening**
- Randomization
- HS-Omega-3 Index Test (fingerstick blood sample)
- Dispense and document dispensing of IP and provide instructions for administration
- Dispense IP diary and provide instructions for use
- AE assessment

